EXCLUSION CRITERIA	
 
Active involvement of the central nervous system with malignancy (previous CNS involvement is allowed if clearance of CNS disease has been documented prior to enrollment)
 
Pregnant or breastfeeding
 
Karnofsky Performance Status < 60%
 
Active leukemia (> 5% leukemic blasts in peripheral blood or bone marrow)
 
Non-hematologic malignancy with a life expectancy of < 5 years
 
Known history of human immunodeficiency virus (HIV) or active hepatitis C virus (HCV) or hepatitis B virus (HBV) infection. Subjects who are positive for hepatitis B core antibody or hepatitis B surface antigen must have a negative polymerase chain reaction (PCR) result before enrollment. Those who are PCR-positive will be excluded.
 
Known bleeding disorders (eg, von Willebrand's disease) or hemophilia.
 
History of other malignancies, except: 
 
Malignancy treated with curative intent and with no known active disease present for <math>\geq</math> 3 years before the first dose of study drug and felt to be at low risk for recurrence by treating physician.
 
Adequately treated non-melanoma skin cancer or lentigo maligna without evidence of disease.
 
Adequately treated carcinoma in situ without evidence of disease.
 
 
 

TREATMENT SUMMARY	Subjects will be treated with ibrutinib 420 mg orally once daily, starting between Day +60 and Day +90 after allogeneic HCT and continuing until 18 months post-transplant
SAMPLE SIZE	50 subjects enrolled and treated
STATISTICAL CONSIDERATIONS	Screening and enrollment of 50 subjects will provide 84% power to detect a decrease in the incidence of relapse at 18 months post-transplant from 45% to 25%

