## **12. STATISTICAL CONSIDERATIONS**

### **12.1 Statistical Design, Effect Size, and Sample Size**

This study is designed as a single-arm efficacy trial using historical published controls. This study's primary endpoint is the incidence of relapse at 18 months after allogeneic HCT for AML/ALL. Baseline relapse rates after reduced-intensity conditioning for these diseases in the published literature vary from 40–60% (1-6). For the purposes of study design, we will use a relatively conservative baseline relapse risk of 45%. This study is designed to detect a decrease in relapse rate from 45% to 25%. Therefore, in the power analysis we will assume that the true relapse rate in the study population is 25%, while the null hypothesis holds that the relapse rate is 45%. Under these conditions, using intent-to-treat analysis, a sample size of 50 enrolled subjects will provide 84% power to conclude that the relapse rate is lower than 45% at the two-sided significance level of 0.05. Conservatively assuming that 45 of these 50 subjects meet the secondary criteria to continue to ibrutinib treatment (Appendix B) and are treated with ibrutinib, a subgroup analysis restricted to these 45 subjects will have 78% power to conclude that the relapse rate is < 45% with a significance level of 0.05.

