## 12.2 Interim analyses

We will monitor major adverse event rates as described above, in particular serious bleeding complications (hemorrhage Grade 3 or 4, as defined by CTCAE v4.0). We will monitor and estimate the incidence rate of serious bleeding in study participants, and report all occurrences and corresponding analytic summaries (such as the estimated incidence rate with 95% confidence intervals) to the DSMB to assist in decision-making regarding early termination for safety.

Allogeneic HCT is an intensive therapy with many associated side effects and toxicities related to the transplant conditioning regimen; the ensuing immunosuppressed status; adverse effects of standard post-transplant medications; and graft-vs-host interactions or GvHD. Toxicities, including Grade 4 toxicities, are relatively common. Non-relapse mortality (NRM) is a definitive endpoint which captures fatal effects of any aspect of the transplant process outside of disease relapse, and thus represents the most accurate and reproducible measure of the toxicity and safety of the allogeneic HCT process.

The baseline cumulative incidence of NRM after allogeneic HCT for acute leukemia with FLU/MEL conditioning was estimated in a recent large cohort study at 20% (22). In order to ensure that patients are not harmed by the study intervention, the formal stopping rule below monitors that the study intervention does not increase the risk of NRM in participants.

The stopping rule is based on the incidence of NRM at 1 year after allogeneic HCT. Patients will be evaluable with regard to the stopping rule if they die or if they reach 1 year post-transplant, whichever occurs first. The stopping rule will be tested every increment of 5 evaluable patients. The stopping rule will be triggered if any of the following conditions are met:

Number of evaluable patients	Number of patients with NRM
5	3
10	5
15	6
20	8
25	9
30	10
35	12
40	13

If the stopping rule is triggered, the study will be terminated, and FDA so notified. This stopping rule provides 80% power to detect an increase in NRM with a type I error rate of 0.05. The stopping rule was constructed using the Pocock boundary with the same significance level for all looks at the data. The rule was created using R v.3.1.3 and the clinfun package.

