### **12.3 Analysis Population**

Subjects who are enrolled but never treated with ibrutinib (eg, due to failure to meet the secondary criteria to continue to ibrutinib treatment) will be included in the primary analysis, which will be performed as an intention-to-treat analysis. However, they will not be counted toward the overall accrual goal of 45 subjects. A planned subset analysis will be performed testing the primary and secondary endpoints in the subset of subjects who receive at least 1 dose of ibrutinib on study.

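### The NRM stopping table ends at 40 evaluable patients although 50 are to be enrolled, and read as printed it does not deliver the stated type I error of 0.05

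*Combined protocol and SAP*

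**What the plan says.** Section 12.2 calls the NRM rule the formal stopping rule. It schedules the looks without an upper limit: "The stopping rule will be tested every increment of 5 evaluable patients". A patient is evaluable on death or on reaching 1 year after transplant, whichever comes first, and the definition is not confined to treated subjects. "The stopping rule will be triggered if any of the following conditions are met", followed by eight rows: 3 of 5, 5 of 10, 6 of 15, 8 of 20, 9 of 25, 10 of 30, 12 of 35 and 13 of 40. There is no row for 45 or 50, and no reason is given for ending at 40.

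The baseline NRM "was estimated in a recent large cohort study at 20" percent. On performance, the section says: "This stopping rule provides 80% power to detect an increase in NRM with a type I error rate of 0.05". On construction: "The stopping rule was constructed using the Pocock boundary with the same significance level for all looks at the data". The NRM rate at which the power is 80% is not stated.

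The number of patients is described in three ways. The Synopsis has "50 subjects enrolled and treated". Section 12.1 has "a sample size of 50 enrolled subjects", of whom 45 are assumed to be treated. Section 12.3 says of subjects who are never treated that "they will not be counted toward the overall accrual goal of 45 subjects".

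**The concern.** A rule that promises a look every 5 evaluable patients should have a threshold at each look the sample can reach. With 50 enrolled, two looks (45 and 50) have none. If only the 45 treated subjects count, one look has none. A committee reaching 45 would not know whether the rule has lapsed or an entry is missing.

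The stated type I error and power belong to a particular set of looks and a particular reading of the entries. If either is unclear, so are those figures, and this is the only NRM threshold in the protocol. Crossing it terminates the study. A false-stop risk well above the stated 0.05 therefore matters as much as a missed signal.

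**Working it through.** **Inputs.** Boundary, baseline NRM of 20%, type I error 0.05 and power 80%: Section 12.2. Enrolment of 50 with 45 treated: Section 12.1. Accrual over 1 year: Sections 3.4 and 12.4.

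**1. Size of the gap.** Counting enrolled subjects, 50 − 40 = 10. Counting treated subjects, 45 − 40 = 5.

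**2. Stated type I error.** Let f(n, x) be the probability of x NRM events among the first n evaluable patients with no earlier stop. Between looks, f(n+5, x) = Σ over j of f(n, x − j) · C(5, j) · p^j · (1 − p)^(5−j), using only paths still below the boundary at n. The type I error is the total probability on or above the boundary over the eight looks at p = 0.20.

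The first look can be checked by hand. If 3 of 5 triggers, P(X ≥ 3) = 10(0.2³)(0.8²) + 5(0.2⁴)(0.8) + 0.2⁵ = 0.0512 + 0.0064 + 0.0003 = 0.0579. That look alone spends more than 0.05.

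| Reading of entries | Type I error at 20% NRM | Where power reaches about 80% |
|---|---|---|
| Stop when the count is reached (as printed) | 0.148 | 35.3% NRM (80.0%) |
| Stop when the count is exceeded | 0.051 | 39% NRM (80.5%) |

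Both readings are consistent with one nominal level at every look: a level between 0.061 and 0.075 gives the entries if they are to be reached, and one between 0.026 and 0.032 if they are to be exceeded. So the Pocock description does not settle the matter. Only the second reading comes near the stated 0.05.

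**3. What rows at 45 and 50 would add if every patient carried the same risk in order.** Entries of 14 of 45 and 15 or 16 of 50 have nominal levels at 20% NRM of 5.2%, 6.1% and 3.1%, in line with the printed rows. Entries are read as counts to be reached.

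| True NRM | 8 looks | 10 looks |
|---|---|---|
| 20% | 14.8% | 15.8-16.6% |
| 30% | 57.8% | 63.8-67.1% |
| 35% | 79.0% | 84.7-87.2% |

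**4. The same comparison under the protocol's evaluability rule.** A death enters the count at once, whereas a survivor enters only at 12 months. With uniform accrual of 50 over 12 months and no deaths, patient 40 is enrolled at 40/50 × 12 = 9.6 months and becomes evaluable at 21.6 months. The last 10 are then alive and 9.6 to 12 months past transplant. With 1-year mortality of 20-40% the average range is about 8.4 to 11.7 months. Little of their first-year risk remains.

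Simulation assumptions: uniform accrual, NRM deaths uniform over the year, 10% relapse deaths, entries read as counts to be reached, added rows 14 of 45 and 15 of 50.

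- 12-month accrual, 8 versus 10 looks: 88.6% and 88.6% at 20% NRM; 98.8% and 98.8% at 30%; 99.7% and 99.7% at 35%.
- Gain with longer accrual: 0.1-0.3 points at 24 months, 0.4-1.3 at 36 months, 0.6-2.6 at 48 months.
- Entries read as counts to be exceeded: gain of 0.0-0.1 points at 12 months and at most 4.6 at 48 months.

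The absolute trigger probabilities move by a few points with the handling of relapse deaths. The near-zero gain at 12 months does not. The high figure at 20% NRM also shows that the binomial type I error in step 2 does not describe the rule when it is applied in calendar time during fast accrual.

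**5. Rows cannot simply be appended.** Two more looks raise the binomial type I error from 0.148 to as much as 0.166 on the first reading, and from 0.051 to 0.059-0.065 on the second.

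**The case against.** The table can be read as the complete look schedule, with 40 as a deliberate last look. That is possible, but the sentence on looks sets no limit and no section explains the end at 40. Equally, the documents do not show that the operating characteristics were worked out for a trial of 40. That would be inference.

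Three stronger readings are tempting, and the documents do not support them.

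- A reader might infer that the last patients are unmonitored. They are not. Section 11.2 provides continuous data monitoring, safety committee contact at least quarterly and status reports to the DSMB. Section 7.2 requires on-treatment deaths to be reported, and Section 12.2 sends serious bleeding data to the DSMB. What is missing is a formal NRM threshold.
- A reader might infer from step 3 a loss of 6 to 9 points of detection at 30% NRM. That treats patients 41 to 50 as carrying the same risk as the rest. Under the evaluability rule and planned accrual they are survivors of most of the year, and the gain is about 0.
- A reader might construct 12 deaths in 40 followed by 10 in 10, or 22 of 50 (44%), with no trigger. This needs ten patients alive near month 10 all to die without relapse before month 12. It is a bound, not a realistic risk.

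It is also fair that a look at 50 comes when accrual is long closed. It is not quite empty: ibrutinib ends at 18 months after transplant (Synopsis, Section 4.2) or after 1 year of treatment (Section 5.1), two statements that differ and need reconciling. Either falls after the 1-year NRM evaluation, so some subjects may still be on drug. A gap larger than 10 would need further assumptions, such as the Synopsis's 50 treated at the assumed 90% continuation rate (50/0.9 ≈ 56 enrolled), and is not established.

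**Conclusion.** The point holds as an inconsistency in the formal safety rule, not as a material loss of protection. The table stops 5 to 10 patients short of the planned sample, depending on who is counted, and contradicts its own look schedule. At the stated 1-year accrual the missing rows cost essentially nothing in the chance of stopping. The cost reaches roughly 1 to 4 points at 30-35% NRM only if accrual takes 3 to 4 years, on the simulation assumptions given.

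The more consequential finding is that the printed counts do not deliver the stated type I error of 0.05 if reaching them stops the trial: the exact binomial value at 20% NRM is 14.8%. A value of about 5.1% requires the entries to be exceeded, which the text does not say. The 80% power cannot be verified without its alternative. The type I error figures assume 20% NRM and patients of equal risk counted in order.

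**What to change.** In Section 12.2:

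- Re-derive the boundary with the same software for the full planned number of evaluable patients, or state that looks end at 40 and why.
- Say whether each entry is a count to be reached or to be exceeded.
- Reconcile the 45 and 50 across the Synopsis and Sections 12.1 and 12.3, and say which subjects count toward the rule.
- Restate the type I error, and the power with its alternative NRM rate, for that set of looks and that reading. Allow for deaths becoming evaluable before survivors, for example by simulation under the planned accrual.

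The cost is a re-run of the boundary code, a short simulation and a few sentences of text. The restated figures may look less favourable than the present 0.05 and 80%.

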### **12.4 Accrual estimates**

We performed 36 reduced-intensity allogeneic HCT for AML/ALL at Stanford in calendar year 2014. We will also plan to open this study at UCSF (with [name]) and City of Hope (with [name]). We anticipate accruing 10 to 15 subjects annually at UCSF and 20 subjects annually at City of Hope, based on their historical transplant patterns. We therefore expect that study accrual will take 1 year to complete.

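### The NRM stopping rule is tested only at each fifth evaluable patient, so the study can run on for up to 2 or 3 evaluable patients after crossing is already certain; a one-sentence addition removes that wait at no cost in error control

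*Combined protocol and SAP*

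**What the plan says.** Section 12.2 (Interim analyses) gives a table of NRM counts at eight looks: 3 of 5, 5 of 10, 6 of 15, 8 of 20, 9 of 25, 10 of 30, 12 of 35 and 13 of 40. The timing is "The stopping rule will be tested every increment of 5 evaluable patients". On who counts: "Patients will be evaluable with regard to the stopping rule if they die or if they reach 1 year post-transplant, whichever occurs first". On the consequence: "If the stopping rule is triggered, the study will be terminated, and FDA so notified". The section states error rates for the rule: "This stopping rule provides 80% power to detect an increase in NRM with a type I error rate of 0.05".

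Section 12.4 says of enrolment: "We therefore expect that study accrual will take 1 year to complete". Section 12.1 plans 50 enrolled subjects.

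Between looks, section 11.2 provides for continuous data review and safety committee calls at least quarterly, and section 7.2 requires deaths to be reported to the monitoring board. Neither section attaches an NRM criterion to that review.

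**The concern.** The limits are cumulative and the count can only stay level or rise. With 3 NRM among the first 3 evaluable patients, the look at 5 will trigger whatever happens to the next two. Read literally, the rule is still not tested until those two become evaluable.

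The evaluability definition makes this more than a formality. A death is evaluable at once, a survivor only at 1 year. For a year after the first transplant, therefore, each newly evaluable patient is a death, and the formal rule waits for further deaths to confirm a settled result. Meanwhile subjects may go on being transplanted on study and started on ibrutinib.

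**Working it through.** **Inputs.** Looks, limits and evaluability come from section 12.2, the 50 subjects from 12.1 and the 1-year accrual from 12.4. Unless stated, a count equal to the listed number triggers the rule.

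**1. The plan's own error figures.** An exact binomial recursion over patients 1 to 40, stopping at the tabulated limits, gives:
- Listed count triggers: type I error at 20% NRM is 0.1477. The first look alone contributes P(X ≥ 3 | n = 5, p = 0.2) = 0.0512 + 0.0064 + 0.0003 = 0.0579. Power of 80% is reached at 35.3% NRM.
- Listed count must be exceeded: type I error is 0.0511, and power of 80% is reached at 38.9%.

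The plan does not state the alternative rate behind its 80%. The stated 0.05 does not reproduce under the first reading; the second comes close. The argument below needs neither figure to be right.

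**2. Why the wait gains nothing.** Let S(m) be the NRM count among the first m evaluable patients, and b the limit at look n. S never falls, so if S(m) ≥ b for some m between the previous look and n, then S(n) ≥ b. The converse holds by taking m = n. Stopping early therefore gives exactly the same set of crossings, for any boundary and any true rate, provided the patients counted early are among those counted at the look.

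The recursion agrees:

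| True NRM | P(cross), looks only | P(cross), early trigger | Mean evaluable at stopping, given crossing |
|---|---|---|---|
| 20% | 0.1477 | 0.1477 | 14.89 → 14.14 |
| 35% | 0.7898 | 0.7898 | 16.52 → 15.61 |
| 40% | 0.9201 | 0.9201 | 14.62 → 13.68 |

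**3. How long the wait can be, in patients.** To be still running after a look, the count there must be at most its limit minus 1. The earliest patient at which the next crossing is certain is therefore: previous look + next limit − (previous limit − 1). For the look at 10 this is 5 + 5 − 2 = 8.

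| Next look | Limit | Earliest certain at patient | Longest wait |
|---|---|---|---|
| 5 | 3 | 3 | 2 |
| 10 | 5 | 8 | 2 |
| 15 | 6 | 12 | 3 |
| 20 | 8 | 18 | 2 |
| 25 | 9 | 22 | 3 |
| 30 | 10 | 27 | 3 |
| 35 | 12 | 33 | 2 |
| 40 | 13 | 37 | 3 |

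In the binomial model, some wait occurs in 51% of crossings at 20% NRM and 61% at 40%.

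**4. How long in calendar time.** This needs assumptions that the documents do not give: uniform entry, constant hazards, 40% NRM and 5–15% relapse mortality at 1 year, and a first dose at Day +75 in all alive. With evaluability as written, simulation gives:
- Listed count triggers: mean wait about 28–44 days (90th percentile about 69–93), with some wait in 80–95% of triggered trials. Enrolment is 50/365 = 0.137 per day, so 28 × 0.137 = 3.8 and 44 × 0.137 = 6.0 further transplants. About 3–5 further first doses fall in the wait.
- Listed count must be exceeded: mean wait about 14–19 days, so 14 × 0.137 = 1.9 to 19 × 0.137 = 2.6 transplants.

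A second model had deaths spread uniformly over the first year, NRM of 20–40%, relapse mortality of 0–30% and accrual over 12 or 24 months. It gave mean waits of about 0.6–2.4 months and about 1.5–9 further subjects.

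**The case against.** The strongest reply is that grouped looks are ordinary practice and the saving is small: under 1 evaluable patient on average in the binomial model, never more than 3, and none in about 40–50% of crossings. Data are reviewed continuously, deaths go to the board, and nothing forbids acting before a look. This stands as far as priority goes. It does not remove the point, because no NRM criterion applies between looks. The cost is also calendar time rather than patient counts: at about one enrolment a week, a wait for one or two evaluable patients can mean several new subjects.

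Three stronger readings are tempting and not supported.
- A reader might infer from the 1-year evaluability that the wait runs to many months. As written it does not, because deaths enter at once. Even if looks were taken in transplant order on complete 1-year status, which is not what section 12.2 says, the mean wait under the same accrual assumptions is about 60 days.
- A reader might take any early cluster, such as 5 NRM among 7, as a state in which the study waits. The table rules that one out: at least 3 of the first 5 would be NRM, and the rule would already have fired.
- A reader might infer that, since the early trigger changes no error rate, the stated 0.05 and 80% are confirmed. They are not. The trigger preserves whatever the boundary delivers, which at the 20% baseline is 0.1477 in the binomial model when the listed count triggers. With evaluability as written, early looks over-represent deaths, and simulated crossing at 20% NRM was about 44–94% depending on assumptions. The high share of trials with a wait in step 4 partly reflects that separate problem.

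**Conclusion.** The point holds and is minor. Section 12.2 lets the study continue after crossing is certain, for at most 2 or 3 evaluable patients, and the wait gains nothing. That conclusion is exact and needs no assumption about rates or accrual.

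Its size in time does rest on assumptions. At 40% NRM, with 50 subjects entering uniformly over 1 year, constant hazards and 5–15% relapse mortality, the wait averages about 28–44 days and 4–6 further transplants, or about 14–19 days and 2–3 transplants if the listed count must be exceeded. The identical crossing probabilities in step 2 come from the binomial model and the day counts from the calendar model; they should not be read as one set of results. The type I error of the table and the timing of evaluability are larger, separate matters that this change leaves untouched.

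**What to change.** Add one sentence to section 12.2:

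> The rule is also triggered between looks as soon as the number of NRM events within 1 year of transplant, among the patients who are counted in the next look, reaches the limit for that look.

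Both restrictions matter. Section 4.2 follows survival to 18 months, so deaths after 1 year need to be kept out of the count. If looks were later redefined by transplant order, counting NRM in every subject against the next limit would raise crossing at 20% NRM from about 15% to about 96% under the accrual assumptions above.

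State that the addition leaves the crossing probability of whatever boundary is used unchanged, and do not restate 0.05 or 80% as verified. Say also whether the listed count triggers the rule or must be exceeded, since that sets the limit to which the sentence refers. The cost is the text alone: deaths are already reported, no data are added, and no power or error control is lost. The sentence carries over to any cumulative boundary, so it can be made together with corrections to the limits and to evaluability.

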### 3.1 Inclusion Criteria

#### 3.1.1 Inclusion Criteria for enrollment (pre-transplant)

- Diagnosis of acute myeloid leukemia (AML), acute biphenotypic leukemia, or acute lymphoblastic leukemia (ALL). CML transformed to blast crisis is eligible.
- Planned allogeneic HCT using FLU/MEL or FLU/BU conditioning (regimens defined below).
- Planned GvHD prophylaxis consisting of TAC/MTX or TAC/SRL (regimens defined below).
- HLA-identical sibling donor, HLA-matched unrelated donor, or donor mismatched at 1 HLA allele or antigen.
- Less than or equal to 5% blasts on bone marrow examination within 60 days of starting conditioning.
- Age  $\geq$  18 years and  $\leq$  70 years.
- Able to give informed consent.

Subjects will be eligible if their planned conditioning regimen for allogeneic HCT consists of one of the two following standard reduced-intensity conditioning regimens:

- FLU/MEL: Fludarabine 120 to 180 mg/m^2; melphalan  $\leq$  150 mg/m^2
- FLU/BU: Fludarabine 120 to 180 mg/m^2; busulfan  $\leq$  8 mg/kg orally or  $\leq$  6.4 mg/kg intravenously

Subjects will be eligible if their planned post-grafting immunosuppression consists of one of the two following regimens:

- TAC/MTX: Tacrolimus (oral or intravenous) and intravenous methotrexate administered according to institutional standard practice.
- TAC/SRL: Tacrolimus (oral or intravenous) and oral sirolimus, administered according to institutional standards of care.

These two regimens of post-grafting immunosuppression have been shown to produce equivalent rates of GvHD, relapse-free survival, and GvHD-free survival in a prospective, randomized controlled trial (16), and we thus view them as equivalent for the purposes of this clinical trial. Immunosuppressant doses and taper schedules will be adjusted based on institutional standard practice and clinical factors, at the discretion of the attending physician, as in previous clinical trials of these regimens (16).

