Serious adverse events (SAEs) CTCAE Grade 3 and above, and all subsequent follow-up reports will be reported to the Stanford Cancer Center Data and Safety Monitoring Committee (DSMC) using the study specific CRF regardless of the event's relatedness to the investigation. Following review by the DSMC, events meeting the IRB definition of 'Unanticipated Problem' will be reported to the IRB using eProtocol within 10 working days of DSMC review, or within 5 working days for deaths or life-threatening experiences. If complete information is not available at the time, the investigator must provide follow-up information as soon as it is known.

Adverse events that are serious and unexpected suspected adverse reactions, and are possibly, probably, or definitely related to the study drug ibrutinib (SUSAR per 21CFR§312.32), will be reported to the FDA via IND Safety Report [21CFR§312.32]

within 14 calendar days, or within 7 calendar days if the event is an unexpected fatal or life-threatening suspected adverse reaction.

In addition, all serious adverse events (initial and follow-up information) will be reported on the Serious Adverse Event Report Form from Pharmacyclics and sent via email or fax to Pharmacyclics Drug Safety or designee within 24 hours of the discovery of the event or information. Pharmacyclics may request follow-up and other additional information from the Investigator (for instance, hospital admission/discharge notes and laboratory results). The contact information (phone, email and fax) for Pharmacyclics Drug Safety can be found on the Serious Adverse Event Report Form and instructions.

Hematopoietic cell transplantation (HCT) is an aggressive therapy for the treatment of a number of life-threatening malignant and non-malignant disorders. Individuals considered for HCT have generally exhausted other avenues of effective therapy. The non-relapse mortality (NRM) associated with a sibling-donor myeloablative allogeneic transplant is approximately 20% and the NRM for an unrelated-donor myeloablative allogeneic transplant ranges from 20-50%. In the setting of reduced-intensity conditioning and allogeneic HCT, the NRM is approximately 10% with a sibling donor and 20% with an unrelated donor.

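### Section 12.2 gives the NRM stopping rule a 0.05 type I error and 80% power without an alternative or an inequality; at 20% NRM the table stops falsely 14.8% of the time if the count is reached, 5.1% if exceeded.

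*Combined protocol and SAP*

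**What the plan says.** Section 12.2 tests 1-year NRM at every fifth evaluable patient. It prints eight pairs of evaluable patients and NRM counts: 5/3, 10/5, 15/6, 20/8, 25/9, 30/10, 35/12 and 40/13.

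- Trigger: "The stopping rule will be triggered if any of the following conditions are met". No inequality sign is attached to the counts.
- Consequence: "If the stopping rule is triggered, the study will be terminated, and FDA so notified".
- Baseline: "The baseline cumulative incidence of NRM after allogeneic HCT for acute leukemia with FLU/MEL conditioning was estimated in a recent large cohort study at 20" per cent. The text then says that the rule guards against an increase in NRM. The 20% is not labelled as the null and carries no time point.
- Operating characteristics: "This stopping rule provides 80% power to detect an increase in NRM with a type I error rate of 0.05". The size of the increase is not given.
- Construction: "The stopping rule was constructed using the Pocock boundary with the same significance level for all looks at the data".
- Who counts: "Patients will be evaluable with regard to the stopping rule if they die or if they reach 1 year post-transplant, whichever occurs first".

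Outside Section 12.2, Section 7.2 says that after reduced-intensity conditioning "the NRM is approximately 10% with a sibling donor and 20% with an unrelated donor", without linking these rates to the rule.

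**The concern.** This is the only formal stopping rule, and crossing it ends the study. A reader who takes a listed pair as a condition that is met when the count occurs will stop at 3 NRM deaths in 5 evaluable patients. At the section's own 20% baseline, that first look alone has a false-stop probability above the whole 0.05 allowed for eight looks.

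A reader who takes the counts as values to be exceeded allows one more NRM death at every look. The section does not settle which reading applies. The 80% power cannot be interpreted or checked without its alternative.

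At 20% NRM the natural reading stops too readily. The main cost is therefore a trial wrongly terminated rather than weaker protection of participants.

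The evaluability definition is a second problem. A binomial boundary assumes that the evaluable patients are an unselected sample. Here a death counts at once, while a survivor counts only after a full year.

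**Working it through.** **Inputs.** The looks, counts, 20% baseline, 0.05 and 80% are all from Section 12.2.

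**Method.** Let f_k(s) be the probability of s NRM deaths at look k without an earlier stop. Each look adds 5 independent patients: f_k(s) = Σ_j f_{k−1}(s−j) · C(5,j) p^j (1−p)^{5−j}. The stopping probability at look k is the sum of f_k(s) over s ≥ b_k. Here b_k is the listed count (reached) or the listed count plus one (exceeded). Paths that stop are removed before the next look.

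**First look by hand, p = 0.20.**
- Reached: P(X ≥ 3 of 5) = 10(0.008)(0.64) + 5(0.0016)(0.8) + 0.00032 = 0.0579.
- Exceeded: P(X ≥ 4 of 5) = 0.0064 + 0.00032 = 0.0067.

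**Cumulative stopping probability, p = 0.20.**

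| Evaluable | Listed count | Reached | Exceeded |
|---|---|---|---|
| 5 | 3 | 0.058 | 0.007 |
| 10 | 5 | 0.073 | 0.011 |
| 15 | 6 | 0.103 | 0.024 |
| 20 | 8 | 0.109 | 0.027 |
| 25 | 9 | 0.122 | 0.034 |
| 30 | 10 | 0.138 | 0.044 |
| 35 | 12 | 0.141 | 0.046 |
| 40 | 13 | **0.148** | **0.051** |

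So at 20% the plan's 0.05 is approximately reproduced by exceeded (0.0511). Reached gives 0.1477, and 0.1477/0.05 is about 3.

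**Other true NRM rates.**

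| NRM | Reached | Exceeded |
|---|---|---|
| 10% | 0.011 | 0.001 |
| 15% | 0.048 | 0.009 |
| 17.5% | 0.087 | 0.023 |
| 30% | 0.578 | 0.391 |
| 35% | 0.790 | 0.642 |
| 40% | 0.920 | 0.837 |

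The probability equals 0.80 at 35.3% (reached) or 38.8% (exceeded). Neither rate is in the protocol, so the 80% can be neither confirmed nor refuted.

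**Does the Pocock construction help?** With a constant per-look level a, the stopping count at each look is the smallest whose binomial tail is at most a. At p = 0.20:
- Reached: a must be at least 0.061, since P(X ≥ 6 of 15) = 0.0611, and below 0.075, since P(X ≥ 11 of 35) = 0.0747.
- Exceeded: a must be at least 0.026, since P(X ≥ 11 of 30) = 0.0256, and below 0.032, since P(X ≥ 8 of 20) = 0.0321.

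Both readings have the constant-level shape, so shape alone does not choose. A per-look level above 0.06, with 0.058 spent at the first look, cannot belong to a rule whose overall error is 0.05. With a 20% null, shape and stated error together exclude reached and allow exceeded.

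**Evaluability.** No survivor can be evaluable until 12 months after the first transplant, so every evaluable patient before then is a death. Section 12.4 expects 1 year of accrual. As an illustration, take 50 patients, 20% NRM, uniform accrual over that year and uniform death times. At 12 months the average follow-up is half a year, so about 50 × 0.20 × 0.5 = 5 NRM deaths are expected. The first look is then likely to consist of deaths only, and it avoids the trigger only if enough of them are relapse deaths.

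Simulations that order patients by the time they become evaluable, with 50 patients and 20% NRM, gave:
- Uniform death times, 1 to 3 years' accrual, relapse deaths 0 to 30% by 1 year: about 0.35 to 0.94 reached, 0.15 to 0.82 exceeded.
- Late deaths (Beta(3,1)), relapse deaths 10 to 30%: about 0.25 to 0.61 reached, 0.09 to 0.34 exceeded.
- Check, ordering the same patients by enrolment: 0.147 and 0.051, matching the exact values.
- Adverse case, with 30% relapse deaths occurring early (Beta(1,3)) and NRM deaths late (Beta(3,1)): about 0.12 to 0.13 reached, 0.045 to 0.055 exceeded. Here relapse deaths dilute the early looks.

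Death timing and the share of relapse deaths are assumptions, as is accrual beyond 1 year. These ranges show a direction, not an estimate.

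**The case against.** The best defence is that Section 12.2 is coherent once the counts are read as values to be exceeded. A 20% null is plainly implied by the baseline and the stated aim. With it, exceeded gives an overall error of 0.051 and a constant per-look level, as described. What is missing is then an inequality sign and the alternative. That much stands, and it is why the point is not simply that the 0.05 is wrong.

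It does not close the matter. The trigger wording reads against it, and no passage confirms it.

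A second defence is that the 20% has no stated time point and comes from a FLU/MEL cohort, while FLU/BU is also admitted. If the true 1-year NRM is lower, so is the error: 8.7% at 17.5% and 4.8% at 15% if reached. That also stands, and it is a reason to name the null.

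A reader might go further and infer a null near 15.2%, where reached gives 0.050. Section 7.2 offers 10% and 20% by donor type, and Section 3.1.1 admits "HLA-identical sibling donor, HLA-matched unrelated donor, or donor mismatched at 1 HLA allele or antigen". But that null is solved backwards from the answer, no donor mix is given, and the table then has no constant exact level. The documents do not support it.

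Third, the evaluability ranges rest on inputs that are mostly absent from the protocol. That is fair as to size. Enrichment of early looks for deaths follows from the definition itself. The false-stop probability rises unless relapse deaths are both more numerous and clearly earlier than NRM deaths.

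**Conclusion.** The rule is under-specified, and its trigger, as naturally read, conflicts with its stated error at the only baseline that Section 12.2 offers: 14.8% against 5%, assuming independent patients and a 20% 1-year null. Read as exceeded, the same table gives 5.1%. If the null is 20%, the natural reading sets the trigger one NRM death too low at every look for the stated error.

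Two stronger conclusions are tempting and not supported. One is that the rule's true error is three times what is claimed; that needs both reached and 20%, and the plan states neither outright. The other is that the table is misprinted by one; that is an inference from the error rate and the Pocock construction, not something the documents say. The mistake could lie in the wording, the table, the null or the 0.05.

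Under either reading, neither independent-patient figure describes the rule as it will be run. The evaluability definition should generally push the false-stop probability higher, by an amount that depends on accrual, death timing and relapse deaths.

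**What to change.** Reconcile the trigger wording, the table, the 20% baseline and the stated 0.05. Name the null and the alternative 1-year NRM, and say whether the count is reached or exceeded. Restate the overall type I error and power of the boundary that is kept, by simulation under the protocol's own evaluability definition, with accrual and death-timing assumptions given. No new boundary is proposed here.

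Possible text, with blanks for the sponsor: *The study stops if the number of NRM events [reaches / exceeds] the listed count. The rule was derived for a null 1-year NRM of [ ]% and an alternative of [ ]%. Under the evaluability definition above, with [accrual and death-timing assumptions], its overall type I error is [ ] and its power is [ ].*

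The cost is a short recomputation and an amendment to one section. The restated figures will probably be less favourable. Confirming exceeded, for example, gives 64% power at 35% NRM with independent patients, against 79% for reached.
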